EuroQoL 5-Dimension Health Questionnaire 5-Level ⁸			X			X	X		X	X	11.3.2.3	
Worst Weekly Pruritus numeric rating scale ⁹ Eczema-related Sleep numeric rating scale ⁹ Patient use of topical treatment ¹⁰	X	X	X	X	X	X	X		X	Х	11.3.2.4	

- 1) Subjects who withdraw from the trial will be followed up as described in Section 10. The final safety follow-up visit will be 16 weeks after the last dose (i.e. 14 weeks after the EOT visit).
- 2) The number of weeks until the EOT visit (2 weeks after the last dose of tralokinumab, maximum 140 weeks) and SFU visit (maximum 154 weeks) for each subject will depend on the time of their trial entry and treatment duration.
- 3) Assessments and procedures to be performed at an unscheduled visit are at the discretion of the investigator. If the unscheduled visit involves administration of rescue treatment, the investigator should make every attempt to conduct efficacy and safety assessments (at least disease severity scores [IGA and EASI], concomitant medications/procedures, and AEs) immediately before administering any rescue treatment (see Section 9.5).
- 4) If the date of a trial visit does not conform to the clinical trial protocol, subsequent visits should be planned to maintain the visit schedule relative to baseline.

Trial ID: LP0162-1337

5) At trial visits, tralokinumab will be injected at the trial site, preferably by the subject or their caregiver, alternatively by site staff. At each trial visit, subjects will be provided with tralokinumab to be administered at home until the next trial visit. In case of intercurrent illness that may compromise the safety of the subject, or fever within 72 hours prior to administration, tralokinumab administration should be rescheduled. If an anaphylactic reaction occurs, blood samples should be drawn for the analysis of serum tryptase (see details in Section 9.2).

- 6) Urine samples will be tested at the trial site (dipstick). In case of abnormal dipstick results, a urine sample will be sent to the central laboratory for microscopic examination (leucocytes, erythrocytes, and casts) (Section 11.4.5).
- 7) Adult subjects from all parent trials, except the LP0162-1334 trial, will perform the DLQI. Subjects from the parent trial LP0162-1334 will perform the CDLQI, independent of the age of the subject during participation in ECZTEND.
- 8) Subjects from the parent trial LP0162-1334 will not perform the EuroQoL 5-Dimension Health Questionnaire 5-Level.

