Weeks since first treatment in LP0162- 1337	-2	0	2	4	8	16	24	32 64 96 128 160 192 224 256	40 72 104 136 168 200 232 264	48 80 112 144 176 208 240	56 88 120 152 184 216 248	Variable ² (max 268)	SFU visit Variable ²	Un- scheduled visit (if applicable) ³	Early termination (if applicable) ¹	References (protocol section)
Visit type	Site	Site	Site	Site	Site	Site	Site	Tele- phone ⁴	Short Site	Tele- phone ⁴	Standard Site	Site	Site			
Visit window (days) ⁵	-3	NA	±3	±3	±3	±3	±3	±3	±3	±3	±3	±3	±3			
Patient-reported	d outcom	es (cont	inued)													
Worst Weekly Pruritus numeric rating scale Eczema-related																
Sleep numeric rating scale	X	X	X	X	X	X	X		X		X	X		X	X	11.3.2.4
Patient use of topical treatment ¹⁴																

- 1) If screening/baseline visits are performed on the same day as visit(s) in the parent trial, the order of assessments should be adhered to, working in parallel for both protocols. Assessments where data are captured in different vendor systems databases (ECG, ePRO, and laboratory tests) need to be completed twice. In such cases, the parent trial assessment should be performed first, followed by the trial LP0162-1337 assessment. For subjects included in the trial prior to protocol version 10, the first visit after May 2021 can be a site visit or a telephone visit.
- 2) Subjects who withdraw from the trial will be followed up as described in Section 10. The final safety follow-up visit will be 4 weeks after the last dose (i.e. 2 weeks after the EOT visit). For subjects from the parent trial LP0162-1334, the maximum number of weeks until the EOT visit will be 114 weeks.
- 3) Assessments and procedures to be performed at an unscheduled visit are at the discretion of the investigator. If the unscheduled visit involves administration of rescue treatment, the investigator should make every attempt to conduct efficacy and safety assessments (at least disease severity scores [IGA and EASI], concomitant medications/procedures, and AEs) immediately before administering any rescue treatment (see Section 9.5).

Trial ID: LP0162-1337

THIS DOCUMENT CONTAINS CONFIDENTIAL INFORMATION AND MUST NOT BE COPIED OR MADE AVAILABLE TO ANY THIRD PARTY WITHOUT THE PRIOR WRITTEN CONSENT OF THE LEO PHARMA GROUP

- 4) For subjects from the parent trial LP0162-1334, the telephone visit should preferably be performed as a video call.

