5.3 Trial rationale

The purpose of this trial is to evaluate the long-term safety of tralokinumab in adult and adolescent subjects as well as to evaluate the continuous response, re-treatment response, and response in tralokinumab-naïve subjects treated with tralokinumab.

Subjects eligible for this trial will have received trial treatment and completed the treatment period(s) in one of the 'parent trials': LP0162-1325, -1326, -1334, -1339, -1341, -1342, -1343, -1346, or the investigator-initiated trial TRA-WEI-0015-I (see inclusion criterion no. 2).

Subjects transferring from a blinded parent trial will enter the extension trial without their individual treatment allocation in the parent trial being unblinded. It is assumed that the majority of the subjects entering into this trial will have received tralokinumab in the parent trial – and will in the investigator's opinion have gained therapeutic benefit from tralokinumab.

Optional use of TCS is included in this trial, as subjects transferring from trials LP0162-1339, -1343, and -1346, and the open-label arms of trials LP0162-1325 -1326, and -1334 will have had this option during their treatment in the parent trial. Furthermore, the intended commercial use of tralokinumab is with or without concurrent use of TCS.

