7.1.4 Safety follow-up period (after last IMP dose)

All subjects will complete an off-treatment follow-up period for the assessment of safety, PK, and ADA.

The timing of the safety follow-up visit depends on the parent trial and on whether the subject has consented to participate after May 2021, as summarised in Panel 8.

Panel 8: Safety follow-up visit

Parent trial	Subject did NOT consent to continue after May 2021	Subject DID re-consent or consent to participate after May 2021
LP0162-1325, -1326, -1334 (adolescents), -1339, -1341, -1342, -1343, -1346, and TRA-WEI-0015-I	16 weeks after last dose	4 weeks after last dose

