10.2.2 Reasons for withdrawal from the trial

Trial ID: LP0162-1337

Subjects will permanently discontinue IMP and be withdrawn from the trial in the event of:

- Anaphylactic reaction or other severe systemic reaction to IMP injection.
- An AE that, in the opinion of the investigator or sponsor's medical expert, contraindicates further dosing.
- Diagnosis of a malignancy during the trial, excluding carcinoma in situ of the cervix, or localised squamous or basal cell carcinoma of the skin.
- Evidence of pregnancy.
- Any infection that is opportunistic, such as active tuberculosis and other infections whose nature or course may suggest an immuno-compromised status.
- Severe laboratory abnormalities:
- Alanine aminotransferase (ALT) or aspartate aminotransferase (AST) values >3×upper limit of normal (ULN) with total bilirubin >2×ULN (unless elevated bilirubin is related to Gilbert-Meulengracht Syndrome).
 - Confirmed AST or ALT >5×ULN for >2 weeks.

Subjects withdrawn from the trial must complete the safety follow-up period as specified in Section 7.1.

Data to be recorded in the eCRF

The primary reason for withdrawal from the trial must be recorded in the medical records and on the end of trial form (see Section 11.8) in the eCRF, where the following reasons are available:

- Lack of efficacy.
- Adverse event.
- Withdrawal by subject.
- Withdrawal by parent/guardian.*
- Lost to follow-up.
- Death.
- Other.

If 'adverse event' or 'other' is selected, a specification must be provided in the eCRF.

^{*}For adolescent subjects as applicable.

Page 75 of 187

Stopping rules are described in Section 10.2.1.

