14.3.8.4 Anti-drug antibodies

The presence of ADAs is an endpoint included to assess the immunogenicity of tralokinumab.

The ADA status will be summarised by treatment in parent trial and visits with ADA measurements according to the following categories:

ADA status	Description
Positive, pre-existing	ADA positive at baseline. No post-baseline ADA response ≥4-fold over baseline titre level. At least 1 non-missing post-baseline ADA assessment.
Positive, treatment-boosted	ADA positive at baseline. At least 1 post-baseline ADA response ≥4-fold over baseline titre level.
Positive, treatment emergent	ADA negative or missing at baseline. At least 1 positive post-baseline ADA response.
Negative	ADA negative or missing at baseline. All post-baseline ADA assessments negative.

For the entire trial, the ADA status will be summarised by treatment in parent trial according to the categories of ADA status as listed above and with the following subcategories of treatment-emergent status:

Date: 21-Feb-2022 Version: 14.0
Page 110 of 187

Treatment-emergent subcategory status	Description
Treatment-emergent, persistent	Positive ADA for at least 2 consecutive visits with ADA measurements, at least 10 weeks apart.
Treatment-emergent, indeterminate	Only the last ADA response positive.
Treatment-emergent, transient	Neither persistent nor indeterminate.

The association of ADA status across the trial (positive versus negative) with AEs/SAEs may be evaluated. The ADA-positive subjects across the trial may in this evaluation be divided into the categories given above. The associations between ADA and AE/SAEs may be summarised for persistently, indeterminately, and transiently positive subjects.

Serum samples that test positive for ADA will be analysed for neutralising antibodies (nAB). The test sample will be deemed positive or negative for the presence of nAB to tralokinumab relative to a pre-determined (in assay validation) statistically derived cut point.

For subjects in the safety analysis set with positive ADA status, the ADA titre, nAB status, tralokinumab concentration, IGA assessment, and EASI assessment will listed by subject and visit. The listing will include information about which parent trial the subjects transferred from and what treatment they received in the parent trial.

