5.8.6 Anti-drug antibodies

The ADA status categories are updated compared to the CTP Section 14.3.8.4 to incorporate ADA data from the parent trial.

The ADA status will be categorized as below, where all ADA assessments from the parent trial and ECZTEND are taken into account. For subjects who received tralokinumab treatment in the parent trial, 'first tralokinumab dose' refers to the first tralokinumab dose in the parent trial, if applicable.

The ADA status will be categorised as follows:

ADA positive

- Pre-existing: At least 1 positive ADA assessment before first tralokinumab dose, no post-tralokinumab ADA response greater or equal to 4-fold over the maximum pre-tralokinumab titre level. At least 1 positive post-tralokinumab ADA assessment.
- Treatment-boosted: At least 1 positive ADA assessment before first tralokinumab dose, at least 1 post-tralokinumab ADA response greater or equal to 4-fold over the maximum pre-tralokinumab titre level.
- Treatment-emergent: All ADA assessments negative or missing before first tralokinumab dose, at least 1 positive ADA response after first tralokinumab dose.
 - Persistent: Positive ADA for at least 2 consecutive visits at least 10 weeks apart.
 - Indeterminate: Only the last ADA response positive.
 - Transient: Neither persistent nor indeterminate.

ADA negative

• All ADA assessments negative or missing. At least one non-missing ADA assessment after first tralokinumab dose.

Perishing ADA

• At least 1 positive ADA assessment before first tralokinumab dose, all ADA assessments negative after first tralokinumab dose.

No post-baseline

• No ADA assessments after first tralokinumab dose.

For subjects with an ADA positive measurement during the trial, the development in EASI and neutralising antibodies (nAB) will be presented graphically and listed (IGA included).

Presentations will only present the total, tralokinumab naïve, re-treated, and continuously treated, not the washed-out subjects.

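### If the optional ADA–adverse event comparison uses one whole-trial ADA label, reactions that force withdrawal will tend to look rarer in ADA-positive subjects

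*Protocol*

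**What the plan says.** Protocol 14.3.8.4 makes the comparison optional: "The association of ADA status across the trial (positive versus negative) with AEs/SAEs may be evaluated". It adds: "The associations between ADA and AE/SAEs may be summarised for persistently, indeterminately, and transiently positive subjects". Under that section, one positive sample after baseline is enough to make a previously negative subject positive for the trial as a whole.

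SAP 5.8.6 revises the categories so that status is set "where all ADA assessments from the parent trial and ECZTEND are taken into account", still with one label per subject. For ADA-positive subjects it plans displays of EASI, neutralising antibodies and IGA, not of adverse events. SAP 5.8.1 has no adverse event breakdown by ADA. Both rows of the table of changes in SAP Section 6 refer to Protocol 14.3.5, so the ADA comparison is not recorded as altered or dropped.

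Other provisions that matter:
- Protocol 10.2.2 requires permanent discontinuation and withdrawal for, among other reasons, "Anaphylactic reaction or other severe systemic reaction to IMP injection".
- ADA is sampled at Weeks 0, 4, 16 and 56, then at intervals of 24 weeks (Panel 4) or 32 weeks (Panel 5), and also at early termination, end of treatment and safety follow-up.
- Protocol 7.1.4: "All subjects will complete an off-treatment follow-up period for the assessment of safety, PK, and ADA". Under Panel 4, "The final safety follow-up visit will be 16 weeks after the last dose"; under Panel 5, "The final safety follow-up visit will be 4 weeks after the last dose".
- Protocol 5.3: "It is assumed that the majority of the subjects entering into this trial will have received tralokinumab in the parent trial".

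**The concern.** A subject who has a treatment-ending reaction while ADA-negative leaves the trial and will rarely be labelled positive later. A subject labelled positive because ADA appeared in, say, year two must have been free of such reactions until then. A whole-trial label credits that event-free time to the positive group. This is immortal-time bias, and it acts in the reassuring direction.

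Protocol 5.6 names hypersensitivity and immune complex disease as potential risks and links the second to antibodies against tralokinumab. A comparison run as worded could support an unsound statement that ADA had no bearing on treatment-ending reactions.

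**Working it through.** The plan gives no ADA incidence, onset time, reaction rate or metric for this comparison, so there is no stated figure to reproduce.

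**Inputs from the documents:** treatment for about 0.5 to 5 years (Protocol 7.1.1); about 1,600 subjects (14.1); the ADA sampling described above; the SAP 5.8.1 incidence rate (subjects with the event per 100 patient-years to first event or end of exposure), taken here as the main metric.

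**Assumed:** follow-up T uniform on 0.5–5 years; reactions at 0.5–2 per 100 patient-years; ADA permanent once present; hazard ratio HR after onset of 1 or 2.

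**Step 1: a single onset time.** If ADA appears at time a and reactions are rare, a positive subject can react only during T − a but contributes T to the denominator:

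rate ratio ≈ HR × (T − a)/T = HR × (1 − a/T)

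With HR = 2, a/T of 0.05, 0.25, 0.50 and 0.75 gives 1.9, 1.5, 1.0 and 0.5. With a = 0 (positive at entry) there is no bias.

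**Step 2: onset spread over the trial.** With a low constant onset rate, the chance of turning positive is proportional to T, and onset falls on average halfway through.
- Mean T = (0.5 + 5)/2 = 2.75; mean T² = (5³ − 0.5³)/(3 × 4.5) = 9.25.
- Positive subjects average 9.25/2.75 = 3.36 years of follow-up, of which 3.36/2 = 1.68 come after onset.
- Rate ratio with HR = 2: 2 × 1.68/3.36 = 1.0.
- Ratio of percentages: 2 × 1.68/2.75 = 1.22.

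Percentages suffer less because subjects followed for longer have more chance both to turn positive and to react, which pulls the other way.

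**Step 3: simulation with the trial's sampling.** This uses Panel 5 visits plus early-termination or end-of-treatment and follow-up samples, with the whole-trial label:

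| ADA onset | Rate ratio, HR 1 | Rate ratio, HR 2 | Ratio of percentages, HR 2 |
|---|---|---|---|
| All positive at entry | about 1.0 | about 2.0 | – |
| Mean 16 weeks | 0.91–0.96 | 1.76–1.85 | 1.77–1.78 |
| Mean 52 weeks | 0.74–0.80 | 1.44–1.51 | 1.55–1.58 |
| Spread, half of positives positive at entry | 0.67–0.74 | 1.31–1.45 | – |
| Spread, 1–5 per 100 patient-years | 0.48–0.54 | 0.93–1.01 | 1.16–1.18 |

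A second simulation used different assumptions: follow-up of 26–268 weeks, other dropout of 0.10 per year, 5% or 20% of subjects prone to ADA, and reactions at 0.01–0.10 per year. For a true doubling it gave rate ratios of 1.78–1.86 (onset Weeks 2–16), 1.29–1.48 (Weeks 16–56), 0.76–0.91 (Weeks 56–136) and 0.93–1.05 (Weeks 0–200). Ratios of percentages ran from 1.17 to 1.88.

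**Step 4: do the late samples rescue it?** They catch ADA already present at the reaction, and without the early-termination sample the bias is larger (0.64–0.76 instead of 0.76–0.91 for onset at Weeks 56–136). They cannot remove event-free time before onset. Of subjects who reacted while negative, only 0.1–1.6% were later sampled positive.

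**Step 5: events that do not end treatment.** At constant hazard the ratio is 1.00–1.01 with no effect and 1.48–1.89 for a doubling: dilution without false protection. If events are five times as frequent in the first 16 weeks, it is 0.94–1.00 and 1.28–1.73.

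**Step 6: the alternative.** Splitting each subject's events and time at the first positive sample returns 0.96–1.06 (truth 1) and 1.90–2.07 (truth 2) across both sets of assumptions at constant hazard.

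**The case against.** The strongest reply is that no planned analysis is shown to be wrong. The protocol says the comparison may be done, the SAP omits it from its outputs, and the natural reading is that the option was not taken up. A reader might infer from the point above that the trial is committed to a biased analysis; the documents do not support that. Nor do they settle the opposite. The SAP supplements the protocol and lists its changes in Section 6, and this comparison is neither specified there nor withdrawn. The only exposure definition available to anyone who runs it is the whole-trial one.

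A reader might also infer that a doubling of risk would be hidden. That happens only on the rate scale and with onset spread over the trial or late. The protocol and SAP also report percentages of subjects, where a doubling stays visible. Most entrants are expected to have had tralokinumab before, which points towards the milder cases.

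The scope is narrow. Immune complex disease is not named in Protocol 10.2.2 and ends treatment only if it is judged to contraindicate dosing or counts as a severe systemic injection reaction. It would also be wrong to infer that safety data would be lost: all adverse events are listed and every SAE has a narrative.

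Finally, the split has weaknesses of its own. In one run, 9–18% of reactions after ADA onset were counted as negative because ADA was first found at early termination. If risk is tenfold for 12 weeks after onset, the first-positive-sample version reads 1.19–1.34, while a midpoint version that uses the early-termination sample reads 1.90–2.20. If reactions are five times as frequent in the first 16 weeks of treatment, the split reads 1.34–1.48 for a true doubling; with onset averaging 16 weeks the whole-trial label is then closer (1.50–1.62). These points stand. They are why the split needs a companion analysis and cautious reading.

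**Conclusion.** The concern holds in conditional form. If the optional comparison is run with one ADA label per subject for the whole trial, withdrawal-forcing reactions are biased towards looking rarer in ADA-positive subjects. The size depends on when ADA appears, which the documents do not give, and rests on the assumed reaction rates and on ADA being permanent. The range runs from negligible, if positives are already positive at entry, to loss of a true doubling on the rate scale, if onset is spread over the trial. The analysis is optional and descriptive and does not touch the primary endpoint. The risk is a misleading summary, so this is a point to consider, not a defect in the trial's main results.

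**What to change.** State in SAP 5.8.6 whether the optional ADA–AE/SAE evaluation will be done. If it will:
- Count events and person-time as ADA-negative until the first positive sample and as positive from then on. Subjects positive from the parent trial enter as positive. TRA-WEI-0015-I subjects can use only their ECZTEND samples, because their parent-trial data are not transferred.
- Give event counts and patient-years with each ratio.
- Show beside it one sensitivity analysis that sets onset midway between the last negative and the first positive sample, including the early-termination or end-of-treatment sample. Sampling gaps of 24 to 40 weeks make this necessary, since the main version misses reactions soon after onset.

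The cost is a few lines of SAP text and one table in two versions, from data already collected. The downside is imprecision. With 1,600 subjects the assumed rates imply only 0.4–8 reactions in ADA-positive subjects with no effect, and 0.7–14 with a doubling. Limits will be wide, and the table should be read with the listings and SAE narratives. Showing counts before and after Week 16 would expose early clustering of reactions, but that is optional at these numbers.

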14.3.9 Pharmacokinetics

Trial ID: LP0162-1337

All the PK samples in the trial are trough samples. The trough concentration (C_{trough}) will be listed and descriptive statistics will be provided.

C_{trough} values from subjects with positive ADA/nAB will be compared with values from subjects with negative ADA/nAB, if data permit.

The PK data may be merged with those from other clinical trials with tralokinumab for a population-based meta-analysis. Results of the meta-analysis will be presented in a separate pharmacometrics report outside of the CTR.

14.3.10 Interim analysis

Interim evaluation and reporting of trial data will be performed (e.g. to support submissions for marketing approval or sharing of results at conferences). This will be documented.

Page 111 of 187

14.3.11 General principles

An observed-cases approach will be used for tabulations of data by visit (that is, involving only those subjects who attended each specific visit).

Categorical data will be summarised using the number and percentage of subjects in each category. Continuous data will be summarised using the mean, median, SD, minimum, and maximum values.

Any changes from the statistical analysis planned in this clinical trial protocol will be described and justified in a protocol amendment, the statistical analysis plan update, or the CTR, depending on the type of change.

